## **Abstract**

Pelvic floor disorders can significantly affect a woman's quality of life, yet many feel uncomfortable openly discussing these topics. Treatments include lifestyle modification, medications, and/or surgery. Decisional conflict arises when patients have difficulty choosing between several viable treatment options. Factors contributing to decisional conflict include biased information, poor peer support, and unaddressed fears. Effective counselling may help address these factors. Objectives of this pilot study are to assess: (1) the impact of a small-group workshop on pelvic floor disorders (urinary incontinence (UI), or pelvic organ prolapse (POP)) on decisional conflict regarding treatment options; and (2) participant satisfaction with the workshop in terms of quality of information shared, comfort with discussing pelvic health in a group setting, and perceived benefits of a nurse continence advisor and psychologist. Women  $\geq$  18 years old with urinary incontinence or pelvic organ prolapse will be randomized at the time of their first urogynecology consultation to usual care or a 90 minute workshop on either UI or POP. Five to 10 women will attend each workshop led by a nurse continence advisor and a psychologist. In both groups, decisional conflict will be measured using the validated Decisional Conflict Scale (DCS) at baseline and at the first follow-up clinic appointment. Satisfaction with the workshop will be assessed by a post-workshop survey. Demographic data will be compared between groups using t-tests for continuous data and chi-square tests for categorical data. Change in DCS score will be compared using t-tests. Linear regression analysis will be performed to identify predictors of decisional conflict. This pilot study will assess the feasibility and acceptability of an educational workshop on pelvic floor disorders and its potential impact on decisional conflict. Results of this study will inform future development of interdisciplinary, patient-centred approaches to enhanced decision making in women's health.

## **I. Rationale and Background Information**

Pelvic floor dysfunction, according to the IUGA (International Urogynecological Association)/ICS (International Continence Society), is a general term encompassing urinary incontinence (UI), pelvic organ prolapse (POP), anal incontinence, sensory abnormalities of the lower urinary tract, defecatory dysfunction, and chronic pelvic pain syndromes. The IUGA/ICS defines the symptoms of pelvic organ prolapse as *a departure from normal sensation, structure or function, experienced by the woman in reference to the position of her pelvic organs*. Objectively, POP is *the descent of one or more of the anterior vaginal wall, posterior vaginal wall, the uterus, or the apex of the vagina*. The IUGA/ICS definition of urinary incontinence is *the complaint of involuntary loss of urine, or the observation of involuntary loss of urine on examination*, and can be sub-categorized further as stress, urge, or mixed urinary incontinence.

Risk factors for UI and POP include age, parity, obesity, and history of pelvic radiation. Bump et al. (1998) proposed a comprehensive model for the development of female pelvic floor dysfunction. In this model, pelvic support and function is influenced by interactions between *predisposing factors* (i.e. race, connective tissue, anatomic, neurologic, genetic), *inciting factors* (i.e. childbirth, nerve injury, muscle injury, radiation, tissue disruption, surgery), *promoting factors* (i.e. constipation, obesity, smoking, medication, comorbidities), *decompensating factors* (i.e. aging, dementia, poor mobility), and *intervening factors* (behavioural modification, pharmacologic, devices, surgical). This model is useful for both understanding the etiology of pelvic floor dysfunction and for developing both primary and secondary prevention strategies to address them.

Pelvic floor dysfunction is common and occurs more frequently in women. Urinary incontinence and pelvic organ prolapse are the two most common manifestations of pelvic floor dysfunction. The prevalence of UI ranges from 13.1-49.7% while the prevalence of POP of any severity is approximately 41%. Cystocele is the most frequently encountered form of POP (34%), followed by uterine prolapse (14%), and rectocele (13%).

Treatment options for UI and POP fall into two modalities: conservative treatment (behaviour modification, pelvic floor muscle therapy, pharmacologic therapies, pessaries) and surgical intervention. Although an initial trial of conservative management is usually undertaken, many women will eventually have surgery. In 1995, the estimated lifetime risk of undergoing one operation for pelvic floor disorders was 11.1% by age 80. Based on current population demographics and the increasing prevalence of obesity, it is projected that over the next five decades the demand for incontinence and prolapse care will significantly increase.

Despite the high prevalence of pelvic floor dysfunction in women, it is well accepted that far fewer seek treatment for their symptoms. Patient-reported barriers to seeking treatment include lack of knowledge about their condition and available treatments, the perception that their symptoms are a normal part of ageing or childbirth, or are not appropriate for medical intervention. Left untreated, the symptoms of pelvic floor dysfunction, can be debilitating, leading to functional decline, social isolation, sexual dysfunction, withdrawal from employment or leisure activities, and loss of independence.

Lack of knowledge about pelvic floor dysfunction, in addition to being a barrier to appropriate treatment, can undermine decision-making and the process of informed consent.

Many patients do not feel adequately informed about their condition and seek additional resources to supplement the counselling provided by their physician. Of 458 consecutive patients presenting to a urogynecology outpatient clinic, only 20% of patients felt they had sufficient knowledge about their diagnosis, and of the 80% who felt inadequately informed, most consulted their primary care physician or used the internet to obtain more information. Nonetheless, women with pelvic floor dysfunction have a desire both to be well informed and involved in decision-making, and most women seeking care for pelvic floor dysfunction prefer an active or collaborative role in decision-making.

An essential component of patient-centered care, *shared decision-making* promotes active participation of the patient in discussing a care plan. Shared decision-making has been defined as ‘*an approach where clinicians and patients share the best available evidence when faced with the task of making decisions, and where patients are supported to consider options, to achieve informed preferences*’. This approach may be especially applicable in clinical situations such as pelvic floor dysfunction, where quality, not quantity, of life is at stake. In these cases, effective counselling and decision-making support is essential for the development of an acceptable treatment plan.

Women presented with several viable treatment options, each with respective drawbacks and benefits, may experience decisional conflict, which can result in emotional distress, isolation, and vulnerability. Decisional conflict can be defined as “*the uncertainty about which course of action to take when choice among competing actions involved risk, loss, regret, or challenge to personal life values*”. Antenatal testing, hormone replacement therapy for menopause, hysterectomy for abnormal uterine bleeding, ovarian cancer screening, and treatment for incontinence are all situations specific to women’s health in which decisional conflict may arise. O’Connor et al. (1995) developed the decisional conflict scale (DCS), a validated scale that measures (a) perceived uncertainty between options, (b) factors contributing to uncertainty (feeling uninformed, unclear about values, unsupported in decision making), and (c) factors contributing to effective decision making (feeling the choice is informed, values-based, likely to be implemented, and satisfaction with the decision). A total decisional conflict score from 0 (no decisional conflict) to 100 (extremely high decisional conflict) is given, as well as five sub-scores for each factor listed above.

Designed to facilitate shared decision-making, decision aids are evidenced-based tools that empower patients to make high quality, well-deliberated and informed decisions. A 2014 Cochrane Review reported high-quality evidence that shared decision-making and decision aids increase patient knowledge about treatment options and reduce decisional conflict; increase participation in decision-making and promote of more accurate perceptions of risk (moderate quality evidence); and increase congruence between the chosen option and patient values (low quality evidence). Decision aids have also been shown to significantly reduce the number of patients choosing major elective surgery (i.e. prophylactic mastectomy for BRCA 1/2 gene carriers, cardiac revascularization, orchiectomy). A large randomized controlled trial of 894 British women with benign abnormal uterine bleeding, found that when nurses administered a structured interview to women immediately before their consultation with the surgeon with the goal of clarifying their preferences for treatment, women were more satisfied with their involvement in decision-making and overall costs were reduced, as women were more likely to

choose conservative therapy over hysterectomy.

Among women making treatment decisions for pelvic floor dysfunction, there is limited data on the impact of shared decision-making or decision aids on decisional conflict. In one recent study, in which 103 women with pelvic organ prolapse were randomized to either standard clinician-led, one-on-one counselling or standard counselling plus a decision aid, the addition of a decision aid to standard counselling did not significantly reduce decisional conflict or influence the choice of conservative treatment over more invasive surgery.

Shared decision-making may be difficult to implement in a busy office practice where information exchange is time-limited. Most studies on shared decision-making have focused on the physician-patient interaction, and as such, the most commonly reported barrier to implementing this practice is lack of time for effective counselling. Recognizing the importance of the entire healthcare team in patient-centered care, interprofessional models of shared decision making have been developed and validated, and may help address this time constraint barrier. Although there is a growing body of evidence to suggest that small-group educational workshops increase patient knowledge about pelvic floor dysfunction and improve symptoms and quality of life, no studies to date have explored how group counselling sessions lead by non-physician health professionals affect decisional making in women with pelvic floor dysfunction.

The interprofessional model proposed by Légaré et al. takes into account three conceptual levels of shared decision making: the individual level, in which the patient, once presented with a decision, collaborates with various healthcare professionals as she progresses through the phases of making choice. The second level takes into account how the interactions between members of different healthcare professions influence the decision-making process. Finally, the third level considers how the team functions within the environment in which it is embedded (health policies, social context, and professional organizations).

This model also explicitly introduces the concept of a “decision coach”, a health professional (often a nurse, social worker, or psychologist) who’s role involves being an empathetic but impartial team member who guides a patient through the decision making process. Decision coaching involves assessing patients’ degree of decisional conflict and factors contributing to uncertainty, delivering decision-making support by providing evidenced-based information or patient decision-aids, ensuring understanding, clarifying values, monitoring progress in decision-making, and screening for barriers preventing implementation of a chosen decision. In the context of pelvic floor disorders, the decision coach may play an important role in guiding women through the decision making process.

There are few studies on how decision coaching can help women with prolapse and incontinence reach a satisfactory decision about treatment. This study aims to use the principals of shared decision making to address decisional conflict surrounding treatment for pelvic floor disorders. Specifically, we will evaluate the feasibility and acceptability of small group workshops on pelvic organ prolapse and urinary incontinence led by a nurse continence advisor and a psychologist (decision coach). We will also assess impact of the workshop on decisional conflict. Results of this study will inform future development of interdisciplinary, patient-centered approaches to enhanced decision making in women’s health.

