## **II. Study Objectives, Hypotheses**

**Primary objective:** To evaluate how a structured workshop on pelvic floor disorders impacts decisional conflict with regard to seeking treatment for pelvic organ prolapse and urinary incontinence.

**Secondary objective:** To assess patient satisfaction with the quality of information shared during the workshop, their comfort with discussing pelvic health in a group setting, and the perceived benefits of a nurse continence advisor and psychologist.

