### **Hypotheses:**

1. A nurse and psychologist-led workshop on pelvic floor disorders will result in decreased decisional conflict compared to standard individual physician-led counselling.
2. Participants will be satisfied with the quality of information shared and will feel comfortable discussing pelvic health in a group setting

**Primary Outcome & Measure:** Change in "Decisional Conflict" between baseline and follow-up, as measured by the Decisional Conflict Scale.

**Secondary Outcome & Measure:** Participant satisfaction with the group workshop. This will be measured using a survey administered immediately following the workshop

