### **III. Study Design and Methodology**

This pilot study will be structured as a randomized control trial in which eligible participants will be recruited at the time of their first urogynecology consultation. Participants will be randomized into two groups: (1) standard care (follow up with urogynecologist as usual) or, (2) a workshop on either urinary incontinence (UI) or pelvic organ prolapse (POP), with a follow-up urogynecologist appointment after attendance at the workshop (Figure 1).

Randomization will be done using a computer generated randomization sequence in blocks of 4 or 6. Sequentially numbered envelopes will contain the randomization result, with the group only revealed at time of randomization. Health care providers will be blinded to the treatment group, but participants will be unblinded to treatment group due to the nature of the intervention.

Patients randomized to the intervention group will be asked to select a workshop on either UI or POP based on which pelvic floor disorder they perceive to be most bothersome. Two identical workshops on different dates will be offered for each topic and participants will be required to attend one to be included in the study.

The workshop will be approximately 90 minutes in length. The first 15 minutes will be an information session on either UI or POP led by a Nurse Continence Advisor. The following 60 minutes will comprise a psychologist-led group discussion. The structured discussion will encourage participants to share experiences, thoughts, and feelings on pelvic floor disorders. Resistances and barriers to seeking treatment will be discussed. Decision-making processes will be explored. During the final 15 minutes, participants will be asked to complete a survey to evaluate the workshop. The survey will assess satisfaction with the information provided, quality of group discussion, comfort level with the group experience, and their satisfaction with the roles of the nurse continence advisor and psychologist.

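### A feasibility aim is stated but no feasibility rate is an outcome, and the rule that workshop-arm women must attend to be included drops randomised non-attenders from one arm only

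*Combined protocol and SAP*

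**What the plan says.** The Abstract gives the purpose as "This pilot study will assess the feasibility and acceptability of an educational workshop on pelvic floor disorders and its potential impact on decisional conflict". Section I says that "we will evaluate the feasibility and acceptability of small group workshops on pelvic organ prolapse and urinary incontinence", and puts impact on decisional conflict second.

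The formal objectives differ. The primary objective in section II is "To evaluate how a structured workshop on pelvic floor disorders impacts decisional conflict with regard to seeking treatment", and the primary outcome is the change in DCS from baseline to follow-up. The secondary outcome is satisfaction with the workshop: "This will be measured using a survey administered immediately following the workshop". The Abstract's own numbered objectives match section II. The Analysis of results section plans baseline comparisons, unpaired t-tests on DCS and a regression for predictors. No consent, attendance, retention or completion rate appears in either place.

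In section III, women already randomised to the intervention choose a UI or a POP workshop, each offered on two dates, and "participants will be required to attend one to be included in the study". Section IV separately excludes, at entry, women who are unable to attend. It bases the sample size on clinic volume and an assumed participation rate of at least 50%.

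**The concern.** A plan that declares a feasibility aim should say which rates answer it and who is in each denominator. This one does neither, and its one rule on attendance works against it. The entry criterion already screens out women who say they cannot come. The section III rule therefore acts on women who said they could come, were randomised, and then did not. For a group session on a sensitive topic, those are the women a feasibility assessment most needs to count.

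The same rule affects the primary outcome. Controls face no equivalent condition, so the comparison becomes workshop attenders against all controls. Women who attend may differ from those who do not in motivation, distress or readiness to decide, and any of these could bear on change in DCS. Randomisation no longer protects that comparison.

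**Working it through.** **1. The plan's own figure.** Section IV: 80 × 0.50 = 40 and 80 × 1.00 = 80 in total; divided by 2, 20 to 40 per group. This reproduces the stated figures. It also equals workshop capacity: 2 topics × 2 dates × 5 to 10 women = 20 to 40. It is recruitment arithmetic, with no power or precision target behind it.

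**2. Stated aims against planned measures.**
- Decisional conflict: measured (DCS in both arms, at baseline and follow-up) and analysed.
- Acceptability: measured by the Post-Workshop Questionnaire, among attenders only.
- Feasibility: no outcome, no analysis, no target. The 50% participation rate is a planning input.

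**3. Effect of the rule on attendance.** Let *a* be the true attendance rate among *n* women randomised to the workshop. The number included is *n·a*, and attendance among the included is *n·a / n·a* = 100% for any *a*. The documents give no value for *a*. Over an assumed 50% to 90%, 10 to 18 of 20 women, or 20 to 36 of 40, would remain, with no matching loss among controls.

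**4. Effect of the rule on the DCS comparison.** Let *q* = 1 − *a*, and let δ be the difference in mean DCS change, without any workshop, between women who would attend and women who would not. The control arm contains both kinds, so attenders minus all controls estimates (effect in attenders) + *q*·δ. With δ = 0.5 SD (an assumption) and *q* from 0.1 to 0.5, the bias is 0.1 × 0.5 = 0.05 SD to 0.5 × 0.5 = 0.25 SD. Its direction is unknown. If δ = 0 there is no bias, but the documents give no grounds for assuming that.

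**5. What the sample could give.** The Wilson 95% interval is [p + z²/2n ± z√(p(1−p)/n + z²/4n²)] / (1 + z²/n), with z = 1.96. For an assumed attendance of 70%:
- 14/20: (0.796 ± 0.223)/1.192 = 48.1% to 85.5%.
- 28/40: (0.748 ± 0.150)/1.096 = 54.6% to 81.9%.

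These are wide but usable. The same widths would apply to follow-up completion in each arm at that rate.

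**6. Context for the DCS test.** The documents state no alpha, sidedness, SD or target effect. Assume two-sided 5%. The normal approximation for 80% power is d = (1.96 + 0.84)√(2/n), which gives 0.89 SD (n = 20) and 0.63 SD (n = 40); the exact t-test gives 0.91 and 0.63. At an assumed 0.5 SD, exact power is 34% (n = 20) and 60% (n = 40). The 95% interval for the difference would be about ±1.96√(2/n) = ±0.62 SD or ±0.44 SD.

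**The case against.** The strongest reply is that feasibility is one of three stated aims and the other two are served. That is right. A reader might infer that the pilot cannot answer its own question at all; the documents do not support this, because decisional conflict is measured in both arms and the questionnaire covers usefulness, length, group size, comfort and willingness to attend again. The limit on acceptability is that only attenders are asked.

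Second, a reader might infer that attendance can never be recovered. That also goes too far. Allocation uses numbered envelopes, attenders complete a survey on the day, and a coordinator approaches candidates in person, so counts could probably be rebuilt. Nothing forbids this, but nothing plans it either.

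Third, the attendance sentence could be read as an expectation set at entry, alongside the exclusion for inability to attend. The wording makes this hard to sustain: the workshop is chosen after allocation to the intervention, and the sentence makes attendance a condition of inclusion. Even on the milder reading, attendance is not a planned outcome.

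Fourth, nobody has promised a definitive trial or a decision based on a p-value. That stands. It would be speculation to say that a null result will be misread, and the SD of DCS change is not missing, since it comes with the planned t-test. At most it is distorted in the workshop arm.

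**Conclusion.** The point holds in limited form. A feasibility aim is declared without any outcome or analysis to serve it. The attendance rule, followed as written, fixes attendance at 100% among included women and exposes the DCS comparison to one-sided exclusion after randomisation. That conclusion rests on the text alone. The sizes rest on assumptions: attendance of 50% to 90%, and a 0.5 SD difference between attenders and non-attenders, give a bias of 0.05 to 0.25 SD in either direction.

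The power figures are context only, since alpha and effect are assumed. It would be too strong to conclude from them that the DCS comparison is worthless or that feasibility must replace it as primary. The documents call the study a pilot and speak of potential impact, and statisticians would differ on which outcome should lead.

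**What to change.** 1. In section III, delete the condition that a woman must attend a workshop to be included. State that every randomised woman stays in her assigned arm, that her follow-up DCS is sought whether or not she attended, and that she is included in the DCS comparison.
2. In section II, add named feasibility outcomes, each with a 95% CI: consent among eligible women approached; attendance among all women randomised to the workshop; follow-up DCS completion by arm among all randomised.
3. Report how many women were excluded at entry for inability to attend, because attendance among randomised women does not capture them.
4. Keep change in DCS as the primary clinical outcome. In the Analysis of results section, report the between-arm difference with its 95% CI and the SD, not a p-value alone.

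Making feasibility the primary outcome is optional.

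The cost is protocol wording and a short recruitment and attendance log for the existing coordinator, with no extra patients or visits. The DCS difference may be diluted: if non-attenders gain nothing, an effect of 0.5 SD among attenders at 70% attendance becomes 0.7 × 0.5 = 0.35 SD. That is the effect of offering the workshop, and the comparison that randomisation supports.
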